### **Subject Recruitment and Compensation**

Describe recruitment procedures, including who will introduce the study to potential subjects. Describe how you will ensure that subject selection is equitable and all relevant demographic groups have access to study participation (per 45 CFR 46.111(a) (3)). Include information about approximately how many DUHS subjects will be recruited. If subjects are to be compensated, provide specific prorated amounts to be provided for expenses such as travel and/or lost wages, and/or for inducement to participate.

Study staff will attend clinic days. Eligible patients of participating clinicians will be identified and informed about the study by the medical assistant. On study days, eligible patients of participating clinicians (who will have been trained on protocol) will be approached consecutively until the end of the clinic day or until target enrollment is complete. A study coordinator will work with the scheduled study clinician(s) and their medical assistant(s) to identify patients who may be eligible before the start of the clinic session. During the vital signs check-in procedures, the medical assistant will inform potentially eligible participants about the study if their check-in BP is  $\geq 140$  mmHg systolic or  $\geq 90$  mmHg diastolic. If an eligible patient is interested in participating, the medical assistant will introduce the patient to the study coordinator who will provide more information and obtain informed consent. Based on the number of patients with hypertension, it is estimated this pilot study will reach target enrollment in 5 or fewer study enrollment days. There is no compensation provided to participants. The ICG assessment will be provided free of charge.

### **Study Interventions**

If not already presented in #4 above, describe study-related treatment or use of an investigational drug or biologic (with dosages), or device, or use of another form of intervention (i.e., either physical procedures or manipulation of the subject or the subject's environment) for research purposes.

If a patient approached by the medical assistant is interested in participating, the medical assistant will “hand-off” the patient to a study coordinator. The study coordinator will obtain informed consent and enter study information into a secure Redcap database. An in-office ICG assessment will then be performed by either the study coordinator or a trained clinic nurse. The procedure uses four electrodes (2 electrodes on the right ankle and 2 electrodes on the left wrist) and takes approximately 5 minutes to perform while the participant lies on an exam table. It is painless and completely noninvasive (does not even require chest to be bare). The ICG report will be printed and presented to the participant’s clinician, who will then see the patient. The report will contain a recommendation for therapy based on the result. Participating clinicians will have all been trained about ICG and how to interpret the report.

Participating patients will be seen in a hypertension follow-up visit 1-month later and have repeat AOBP measured in the office. If BP is  $<140/90$  mmHg, they will continue the current BP-lowering medication regimen and follow-up per usual care. If AOBP average is  $\geq140/90$  mmHg, the participating patient will have repeat ICG and therapy adjustment as above with another one-month follow-up. The four-month visit AOBP average will be used as the endpoint for this pilot study. For participants whose office BP is controlled prior to the 4-month visit, we will conduct a chart review to assess last clinic BP obtained, which will be entered into REDCap.

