# The Duke Primary Care Tailored to You (TTY) Blood Pressure Control Pilot Study

## Research Summary

### Research Abstract

Suboptimal blood pressure (BP) lowering therapy is a key reason for failing to reach hypertension control targets. Both clinical inertia and patient adherence contribute to suboptimal BP-lowering therapy. Impedance cardiography (ICG) is a simple, noninvasive method to assess a person's hemodynamic state and the pathophysiology contributing to high BP. Armed with such an understanding, a clinician can tailor medication selection to the individual patient. In this pilot study, we will test a protocol and procedures designed to investigate the clinical utility and feasibility of ICG-based hypertension therapy in the primary care setting. Twenty patients with uncontrolled hypertension (office BP $\geq$ 140/90 mm Hg) who are taking at least one BP-lowering medication will be enrolled in this study and followed for four-months. Participants will undergo ICG in the office setting during their clinic visit, and ICG assessment will be used to guide medication selection. Follow-ups with repeat BP measurement and ICG-guided medication titration will occur monthly until BP is controlled or four-months have passed. Outcomes (at four months) will be percent of patients who attain controlled BP and mean BP achieved as well as feasibility outcomes (enrollment and completion rates). This study is low-risk, carrying the same risks as standard care for patients with hypertension. Participants' BP will continue to be monitored in the standard manner in addition to ICG assessment.

*Primary study objectives:* To test procedures and gather preliminary data on the potential efficacy of incorporating impedance cardiography (ICG) into the assessment of patients with hypertension in the primary care setting to provide the clinician guidance on individualizing therapy to improve blood pressure (BP) control. Potential efficacy will be assessed as percentage of participants in whom BP control is attained.

*Secondary study objectives:* Collect preliminary data for informing a larger study.

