For participants whose office BP is controlled prior to the 4-month visit, we will conduct a chart review to assess last clinic BP obtained, which will be entered into REDCap.

We will conduct anonymous surveys with both patients and providers who participated in the study to better understand acceptability and feasibility. These will be administered using REDCap and will include a short implied consent statement.

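### The BP outcome is dated at four months, but participants controlled earlier have no scheduled month-4 reading, and the undated chart value that evidently replaces it can be the reading that released them

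*Protocol*

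**What the plan says.** Three parts of the protocol bear on this.

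- **When the outcome is measured.** Study Interventions: "The four-month visit AOBP average will be used as the endpoint for this pilot study". The Research Abstract agrees: "Outcomes (at four months) will be percent of patients who attain controlled BP and mean BP achieved". Data Analysis also places both percent at goal and mean BP reduction at four months.
- **When study visits end.** Research Abstract: "Follow-ups with repeat BP measurement and ICG-guided medication titration will occur monthly until BP is controlled or four-months have passed". Study Interventions says that participants below 140/90 at a follow-up visit "they will continue the current BP-lowering medication regimen and follow-up per usual care".
- **What is recorded for those who leave early.** Study Interventions: "For participants whose office BP is controlled prior to the 4-month visit, we will conduct a chart review to assess last clinic BP obtained". Design & Procedures and Data Analysis repeat the sentence.

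The primary objective in the Research Abstract adds: "Potential efficacy will be assessed as percentage of participants in whom BP control is attained". The secondary objective is: "Collect preliminary data for informing a larger study".

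**The concern.** A participant below 140/90 at month 1, 2 or 3 has no study visit at month 4, so the named endpoint does not exist for that person. The chart value has no date, no window, no requirement to postdate the releasing visit, and no rule for a chart with nothing later in it.

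That the chart value stands in for the endpoint is an inference. It is the evident one: the sentence directly follows the endpoint in Study Interventions and the four-month analysis in Data Analysis. If it is not the substitute, these participants have no four-month outcome at all.

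Where the latest chart reading is the releasing one, the participant is at goal by construction. Entry requires a high reading and follow-up stops at the first low one, so visit-to-visit variability alone would produce apparent control. A confidence interval would show the sampling error of 20 patients but not this bias. A later chart reading from some other date can err in either direction.

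**Working it through.** The protocol gives no figure to reproduce: 20 participants are planned without a precision calculation, and no hypothesis is tested.

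**Direction.** Compare the two rules in the same people. Those not released before month 4 count identically under both. Those released and lacking a later reading always count as controlled under the chart rule, but under the month-4 rule only if they are then below 140/90. So

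excess in control rate = r × q × u,

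where r is the share released at months 1 to 3, q the share of those with no later reading (taken as unrelated to u), and u the share of released participants who would read at or above goal at month 4. No term can be negative.

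**Size, by simulation.** The protocol supplies the 140 mmHg threshold, entry on a high reading, monthly visits to month 4, and the 75.1% network control rate (Background & Significance). Assumed: systolic BP only, normal distributions, between-patient SD 12, visit SD 7 to 11, no drift after release. The population mean is set so that 75.1% of readings fall below 140. For visit SD 9 that is 140 − 0.678 × √(12² + 9²) = 129.8 mmHg. The 75.1% is network-wide and does not describe this clinic's medicated patients, so absolute rates are not predictions.

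No treatment effect, q = 1:

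| Entry | Visit SD | True month-4 control | Releasing reading carried | Excess (points) | SBP fall overstated (mmHg) |
|---|---|---|---|---|---|
| one high reading | 7 | 36.6% | 65.4% | 28.7 | 3.5 |
| one | 9 | 43.8% | 75.3% | 31.5 | 4.8 |
| one | 11 | 49.5% | 82.3% | 32.8 | 6.1 |
| two high readings | 7 | 23.6% | 51.5% | 27.9 | 3.4 |
| two | 9 | 30.2% | 62.7% | 32.5 | 5.0 |
| two | 11 | 36.2% | 71.9% | 35.7 | 6.6 |

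Check by formula (visit SD 9, one reading): r = 0.70, q = 1, u = 0.45, giving 0.70 × 0.45 = 0.315. With q = 0.5 the excess halves to about 16 points.

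**Sensitivity, q = 1.**

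- Between-patient SD 8 to 15, no effect: 23 to 38 points.
- Mean 145, SD 10, visit SD 6, no effect: 20 points.
- Mean 140, SD 12, visit SD 5 to 12, no effect: 19 to 33 points.
- Constant true effect of −5, −10, −15 or −20 mmHg from month 1 (visit SD 9, one-reading entry): 28, 20, 13 and 7 points.
- Fall of 0, 3, 5 or 10 mmHg per adjustment, which is closer to the protocol's repeated adjustments (same SDs): 31, 30, 27 and 17 points with one-reading entry; 33, 36, 33 and 23 with two.

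**If every released participant has a later reading.** An unbiased one gives 43.7% against a true 43.8%, so no excess. One averaging 5 mmHg above or below the month-4 value shifts the rate by about −12 or +12 points.

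**Sampling error for comparison.** 1.96 × √(0.44 × 0.56 / 20) = 0.218, about ±22 points.

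**The case against.** The strongest reply is that the chart review is a search for a later usual-care reading. Study BP is already held in REDCap, so no review would be needed to recover the releasing value, and these patients remain under a primary care clinician. On that reading the releasing value enters only by default. This stands: the inflation is conditional and its size unknown. It does not remove the default, and it leaves the date of any later reading uncontrolled.

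Second, windows and missing-value rules often sit in a SAP, which is not shown here. That is fair for those rules, but a SAP cannot create a month-4 reading that the visit schedule omits.

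Third, the magnitudes depend on the model. The decline under a constant effect is specific to that assumption; with a fall per adjustment the excess stays between 17 and 36 points. The decline should not be relied on as reassurance.

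Fourth, this is a single-arm pilot of 20 whose main outcomes are enrollment and completion. Selection on a high reading already brings regression to the mean, which a month-4 visit would not remove: the model shows 44% control with no effect at all. Both points are correct and limit the consequence. The carried reading is a further and avoidable error on top.

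Finally, control being 'attained' could mean ever reached. The releasing reading is then valid, but it answers a different question from the four-month outcome stated elsewhere.

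**Conclusion.** The concern holds. It is certain from the text that the stated endpoint is not scheduled for participants controlled early and that the chart value has no date rule. That this value replaces the endpoint is inferred. The upward bias arises only for released participants with no later reading and is proportional to their share. At the extreme of none having one and no treatment effect, the excess is 28 to 36 points with between-patient SD 12 and 19 to 38 points over all populations tried, with the mean systolic fall overstated by 3.4 to 6.6 mmHg (between-patient SD 12). These are upper illustrations on assumed SDs. The damage is limited to the preliminary BP estimates, but they serve the primary objective and feed the planning of a larger study. It should be fixed; it does not undermine the feasibility aims.

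**What to change.** Schedule one month-4 office AOBP for every participant, for outcome measurement only, and use it as the endpoint for all. Align the Research Abstract, Design & Procedures, Study Interventions and Data Analysis. Report 'ever below 140/90' separately under that name.

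If a visit is not possible, take the chart AOBP nearest month 4 within a stated window (for example 17 weeks ± 3), never the releasing reading, and record its date. Report how many participants lack one, and give the observed-only rate with bounds counting all missing as uncontrolled and all as controlled.

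**Cost.** One short uncompensated visit per released participant. AOBP is already the clinic standard. In the model (between-patient SD 12) this is about 9 to 15 of 20 participants with no effect, and 17 to 20 with a constant effect of −5 to −20 mmHg (visit SD 9, one-reading entry). The extra visit can change the completion rate, a main outcome, so completion must be defined to match. The reported control rate may look less favorable.

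The chart fallback is weaker. With half of released participants missing and no effect (visit SD 9, one-reading entry), true control is 44%, observed-only reads 38%, and the bounds are 25% and 60%. At a constant −10 mmHg the figures are 74%, 71%, 38% and 84%.

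The change concerns measurement and says nothing about treatment.

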### **Data Analysis**

As this is a pilot study for feasibility, our main outcomes will be enrollment and completion rates. Nonetheless, we will assess improvement in BP control (both percent at goal  $<140/90$  mmHg as well as average mmHg reduction in BP) at 4-months. For participants whose office BP is controlled prior to the 4-month visit, we will conduct a chart review to assess last clinic BP obtained, which will be entered into REDCap. Characteristics of participants will be tabulated by simple means and percentages. We will also tabulate number and categories of anti-hypertensive medications participants are prescribed.
